#### 1. OBJECTIVE:

The purpose of this study is to evaluate the effect of angle kappa in outcomes, patient satisfaction and visual disturbances in patients with and without astigmatism implanted bilaterally with the PanOptix toric and non-toric IOL after routine cataract surgery as well as to evaluate intraocular (IOL) calculation formulas.

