#### 2. STUDY DESIGN AND METHODS:

- **2.1. Test article:** AcrySof® IQ PanOptix IOL (TFNT00 and TFNTx0 Alcon Laboratories).
- **2.2. Study Design:** Prospective, single center, bilateral eye study.

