#### 3.2. Surgery Procedures:

[figure not shown]
Patients will be received either a non-toric or toric PanOptix IOL based on the amount of astigmatism. Target refraction OU plano ( $\pm 0.25$  D).

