#### 3.4. Measurements and evaluations

1. Visit 1: Informed consent process will be conducted at this visit. Assessments include best-corrected Snellen visual acuity, manifest refraction, intraocular pressure (IOP) using Goldman tonometer, slit lamp examination including dilated fundus exam,

- 2. Visit 2: The surgeon may use his preferred cataract extraction technique (manual or laser). The lens will be implanted in the bag. The following information will be captured the day of surgery: phaco technique (manual or laser), lens implanted and power, target refraction for IOL power implanted using Barrett Universal II, Hill RBF, Holladay 2, Holladay 1 and SRK-T formulas, residual astigmatism and axis for Barrett Toric Calculator and Barrett TK for toric power calculation (if applicable), additional surgical procedures, intraoperative complications, and any device deficiencies. The surgeon's standard post cataract surgery treatment will be used in all patients.
- 3. Visit 3: Slit lamp examination, manifest refraction, UCVA, BCVA, UCIVA (at 60 cm), DCIVA (at 60 cm), UCNVA (at 40 cm) and DCNVA (at 40), and UCNVA at best distance, IOP, IOL orientation, dilated fundus exam (as deem necessary by the investigator), angle kappa measured using OPD III scan, visual symptoms, patient satisfaction and spectacle independence questionnaires, adverse events and any device deficiencies.

All adverse events and complaints will be monitored and recorded at all study visits.

**Table 1.** Visits and Study Assessments

	Visit 1 Screening	Visit 2 and 2A DOS	Visit 3 3-Month 90 ±15 days
Informed Consent	X		
Inclusion/Exclusion	X	X	
Demographics/PMH/Ocular history	X		
Snellen BCVA	X		
Snellen Manifest refraction	X		
UCVA ETDRS (4m)			Χ*
Manifest refraction – Max Plus			X
BCVA ETDRS (4m)			Χ*
UCIVA ETDRS (60 cm)			Χ*
DCIVA ETDRS (60 cm)			Χ*

UCNVA ETDRS (40 cm)			X*
DCNVA ETDRS (40 cm)			Χ*
UCNVA at best distance			Χ*
Intraocular Pressure (Goldman)	X		X
SLE	X		X
Dilated fundus exam	X		χ†
Cataract density / type	X		
OPD III scan	X		X
IOL Power calculation using different formulas	X		
Toric IOL calculation	X**		
Intraoperative data		X	
Toric IOL position		X**	χ†
Questionnaires	X		X
AE/Device deficiencies		X	X

8

X To be performed as scheduled

- \* Monocular and binocular testing
- \*\* If a toric lens is used
- † To be performed as deem necessary by the investigator

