#### 5. STATISTICAL CONSIDERATIONS

#### 5.1. Sample size

A total of 30 subjects will be enrolled. In order to calculate the sample size, we need to know an accurate estimate of the standard deviation of the outcome measure which we do not know; therefore, we consider this study a pilot trial. When estimating the sample size for a pilot study, the simplest method is to apply a sample size rule of thumb. Browne suggests a general flat rule to 'use at least 30 subjects or greater to estimate a parameter'.

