#### 5.2. Statistical Analysis

All data will be collected by the site and entered into a database. Subjects will be assigned an ID number. Data analysis will be performed without patient identification. Statistical analysis will be performed using standard descriptive statistics. Analysis will include stratification based on the amount of preoperative angle kappa as follows: 0 to < 0.3 mm, 0.3 mm to < 0.4 mm and 0.4 mm or higher. Data analysis will be conducted by a third-party consultant.

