#### 2. Secondary Endpoints:

- a. Proportion of eyes within ±0.50 D of intended target (plano) when using the Barrett Universal II formula for IOL power calculation
- b. Proportion of eyes within  $\pm 0.50$  D of intended target (plano) when using the Hill RBF formula for IOL power calculation
- c. Proportion of eyes within ±0.50 D of intended target (plano) when using the Holladay 2 formula for IOL power calculation
- d. Proportion of eyes within ±0.50 D of intended target (plano) when using the Holladay 1 formula for IOL power calculation
- e. Proportion of eyes within ±0.50 D of intended target (plano) when using the SRK-T formula for IOL power calculation
- f. Proportion of eyes with residual astigmatism of 0.50 D or less when using the Barrett Toric Calculator
- g. Proportion of eyes with residual astigmatism of 0.50 D or less when using the Barrett TK for toric power calculation

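### The five formula endpoints need a per-formula prediction error, and their ±0.50 D proportions should be shown with and without each formula's mean error

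*Combined protocol and SAP*

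**What the plan says.** Section 1 (Objective) ends with the aim "as well as to evaluate intraocular (IOL) calculation formulas". Section 5.3 meets it with five secondary endpoints, (a) to (e), identical except for the formula named. The last is "Proportion of eyes within ±0.50 D of intended target (plano) when using the SRK-T formula for IOL power calculation".

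Section 3.2 sets "Target refraction OU plano" with a tolerance of 0.25 D either way. Section 3.4 records on the day of surgery the "target refraction for IOL power implanted using Barrett Universal II, Hill RBF, Holladay 2, Holladay 1 and SRK-T formulas", and a manifest refraction at Visit 3. Section 5.2 gives the method as "Statistical analysis will be performed using standard descriptive statistics", adding only strata by angle kappa. Section 2.2 describes a "Prospective, single center, bilateral eye study", and Section 8.3 marks assignment to groups as not applicable.

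The documents do not mention lens constants, mean prediction error, or any measure of a formula's scatter. They also do not say that performance with constants as supplied is the intended question.

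**The concern.** Two things stand between the endpoint and its purpose.

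**The error is not defined per formula.** The endpoint measures distance from plano. Each eye receives one lens and ends with one refraction, and no eyes are assigned to formulas. Scored against plano, the same eyes pass or fail whichever formula is named, so the five proportions are one number repeated.

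**The natural repair leaves offset and scatter mixed.** Section 3.4 captures what each formula predicted for the implanted power, so achieved minus predicted refraction is the obvious per-formula error. The share of eyes inside a fixed ±0.50 D band then depends on both the mean and the SD of that error. A mean offset may come from the lens constant, from the formula itself, or from the site (for example its refraction method). Scatter is what remains when the mean is removed. With one site and one lens family, a systematic offset does not average out over eyes.

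At stake is what a reader may conclude from five parallel proportions: a lower figure could reflect poorer prediction or an offset that can be corrected, and the planned output would not show which.

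**Working it through.** **Inputs from the documents.** The band is ±0.50 D (Section 5.3). Section 5.1 states "A total of 30 subjects will be enrolled", so with both eyes there are up to 30 × 2 = 60 eyes. That number rests on a pilot rule of thumb, so there is no power calculation to reproduce. On the SD, Section 5.1 says "we need to know an accurate estimate of the standard deviation of the outcome measure which we do not know".

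**Assumptions.** Prediction errors are normal with SD s of 0.35 to 0.45 D. The mean offset m runs from 0 to 0.30 D. For the paired comparison, the correlation between two formulas' errors in the same eye is 0.8 to 0.95 and the fellow-eye correlation is 0 to 0.5.

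**Step 1: share of eyes inside the band.**

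P(|error| ≤ 0.50) = Φ((0.50 − m)/s) − Φ((−0.50 − m)/s)

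For s = 0.40 and m = 0: Φ(1.25) − Φ(−1.25) = 0.894 − 0.106 = 78.9%. For m = 0.20: Φ(0.75) − Φ(−1.75) = 0.773 − 0.040 = 73.3%.

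| SD (D) | m = 0 | 0.10 | 0.20 | 0.25 | 0.30 |
|---|---|---|---|---|---|
| 0.35 | 84.7% | 83.0% | 78.2% | 74.6% | 70.5% |
| 0.40 | 78.9% | 77.5% | 73.3% | 70.4% | 66.9% |
| 0.45 | 73.3% | 72.2% | 68.8% | 66.3% | 63.4% |

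Reading across, 0.10 D costs 1 to 2 points, 0.20 D about 4 to 7, 0.25 D about 7 to 10, and 0.30 D about 10 to 14. Of 60 eyes, 0.20 D moves about 3 to 4 and 0.30 D about 6 to 9.

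**Step 2: can a more precise formula score lower?** Compare SD 0.35 with an offset against SD 0.40 with none (78.9%). The two shares are equal at an offset of about 0.19 D. Above that, the more precise formula has the lower expected share.

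**Step 3: set this against sampling noise.** I simulated 30 subjects with two eyes each, 20,000 runs per setting, both formulas with SD 0.40 D. The SE of the paired difference in proportions was:

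- no offset: about 3.9 to 5.8 points;
- 0.20 D: about 5.6 to 6.9 points, against a loss of 5.5;
- 0.25 D: about 6.2 to 7.3 points, against a loss of 8.5, or 1.2 to 1.4 SE.

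The SE rises with the offset because more eyes are classified differently by the two formulas.

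**Step 4: effect on the order of two formulas** (between-formula correlation 0.9, fellow-eye correlation 0.5).

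| Case | Ranks lower, raw | After subtracting each mean error |
|---|---|---|
| Equal SD 0.40, no offset | 43% (ties about 14%) | 43% |
| Equal SD 0.40, one offset 0.10 D | about 54% | 43% |
| Equal SD 0.40, one offset 0.20 D | 77% | 43% |
| Equal SD 0.40, one offset 0.30 D | 93% | 43% |
| SD 0.35 with 0.25 D offset, against SD 0.40 | about 69% | about 8% (ranks higher in about 86%) |

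After zeroing, two equally precise formulas score about 79.5% each, against a true 78.9%. Subtracting the in-sample mean is therefore optimistic by about 0.6 points here.

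**The case against.** The best case for the plan has four parts.

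- **The plan ranks nothing.** It lists five descriptive proportions, with no between-formula test or decision rule. That is correct. A reader might infer that the study will name a best formula and that its ranking is already wrong; the documents do not support this. What stands is narrower: five parallel figures under an aim to evaluate formulas will be read against each other.
- **The offset need not come from the lens constant.** A reader might infer that any offset is an artefact of the constant and says nothing about the formula. The documents give no basis for that. A formula may be truly biased in these eyes, and the site's refraction method could shift all five together. Removing the mean would hide real bias, so the zeroed figure should not replace the raw one or be the sole basis of a comparison.
- **The effect may be small.** At 0.10 D it is well inside the noise, at 0.20 D about one SE, and only at 0.25 D or more does the loss exceed the SE. Nothing shows that any formula has such an offset at this site. This stands as a limit on size, but the planned output would not report the offset either way.
- **Raw accuracy is a legitimate question, and zeroing can be done later because the predictions are captured.** Both are true. But the plan does not say raw accuracy is the question, does not record the constants, and as literally worded does not yield five distinct proportions.

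**Conclusion.** The point holds in a limited form. As worded, endpoints (a) to (e) either return the same proportion five times or, under the prediction error that the Section 3.4 data support, mix mean offset with scatter. In the second case an equally or more precise formula could look worse. The effect is negligible near 0.10 D and comparable with sampling noise around 0.20 D. It is larger than the noise, though still under 1.5 SE, at 0.25 D. The SDs, offsets and correlations are all assumed, as is normality, because the documents give none. The documents do not show that a misranking will occur.

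These are secondary, descriptive endpoints in a self-described pilot. The primary endpoint is untouched, and no change to the 30 subjects follows. They are, however, the only endpoints comparing the general lens-power formulas named in the plan, so the correction is worth making before analysis.

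**What to change.** In Section 5.3, secondary endpoints (a) to (e):

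1. Define the error for each formula as the Visit 3 manifest spherical equivalent minus that formula's predicted refraction for the implanted power.
2. Record the lens constant used with each formula, where one applies.
3. Report each formula's mean signed error and SD.
4. Give the ±0.50 D proportion twice: raw, and after subtracting that formula's own mean error.
5. State that any sentence comparing formulas will show both versions and will not rest on the raw proportion alone.

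The cost is a little more analysis and one added data item, the constant. The predicted and achieved refractions are already collected, so no visit or subject is added. The drawback is that the zeroed figures are fitted to the same eyes and slightly optimistic, and they remove true formula bias along with any error in the constant. That is why the raw proportion and the mean error stay beside them.

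### Endpoints f and g judge the two toric calculators only by a yes/no at 0.50 D; adding a paired prediction error in dioptres would use data already collected and give more precision

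*Combined protocol and SAP*

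**What the plan says.** All references are to the combined protocol and SAP.

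- **Section 5.3, secondary endpoints.** Endpoint f is "Proportion of eyes with residual astigmatism of 0.50 D or less when using the Barrett Toric Calculator". Endpoint g is "Proportion of eyes with residual astigmatism of 0.50 D or less when using the Barrett TK for toric power calculation". No mean, median or within-eye difference in dioptres is named.
- **Section 3.4.** When a toric lens applies, the day-of-surgery record includes "residual astigmatism and axis for Barrett Toric Calculator and Barrett TK for toric power calculation". Visit 3 includes a manifest refraction.
- **Section 5.2.** The analysis is standard descriptive statistics, carried out by a third-party consultant. No test, significance level or interval is given.
- **Section 5.1.** "A total of 30 subjects will be enrolled". The study is called a pilot because, for a sample size calculation, "we need to know an accurate estimate of the standard deviation of the outcome measure which we do not know". The number follows a rule of thumb: "use at least 30 subjects or greater to estimate a parameter".
- **Section 3.2.** "Patients will be received either a non-toric or toric PanOptix IOL based on the amount of astigmatism". How many eyes will be toric is not stated.
- **Section 1.** Evaluating the lens calculation formulas is part of the study's purpose.

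**The concern.** Endpoints f and g are the only endpoints that address the toric calculators. Each turns a quantity measured in dioptres into a yes or no. An eye at 0.05 D counts the same as one at 0.50 D, and an eye at 0.55 D the same as one at 2.00 D. Both calculators are recorded for the same eye, so the two proportions can differ only through eyes that fall on opposite sides of the cut.

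The stake is how precisely a small toric subset can describe the two calculators. The sample size section names an unknown SD as the reason for running a pilot. Proportions alone would not supply an SD in dioptres for planning a later study. A continuous summary is not ruled out by section 5.2. But if it is not named in advance, the consultant need not produce it, and one produced later would be a post hoc choice.

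**Working it through.** **The plan's own figure.** The 30 subjects equal the rule of thumb quoted in section 5.1. There is no SD, effect, significance level or power behind it, so nothing further can be reproduced. Two eyes each gives at most 2 × 30 = 60 eyes, of which the toric eyes are an unstated part.

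**Step 1: what the cut costs for one calculator.** Let p be the share of eyes at or below 0.50 D. The documents give no p, so 0.50 to 0.90 is assumed. Relative information is that of the yes/no divided by that of the dioptre value; the loss is one minus it.

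*Normal values, known SD, shift in mean:* φ(z_p)² / [p(1 − p)].

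- p = 0.50: 0.3989² / 0.25 = 0.637, loss 36%
- p = 0.80: 0.2800² / 0.16 = 0.490, loss 51%
- p = 0.90: 0.1755² / 0.09 = 0.342, loss 66%

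Magnitudes cannot be negative, so other models were tried:

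| Model | p = 0.50 | p = 0.80 | p = 0.90 |
|---|---|---|---|
| Normal, shift in mean | 36% | 51% | 66% |
| Normal, SD unknown, estimating p itself | 36% | 34% | 38% |
| Rayleigh, change in scale | 52% | 35% | 41% |
| Half-normal, change in scale | 63% | 37% | 36% |

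As one example, the Rayleigh entry uses u = −ln(1 − p) and (u·e^−u)² / [p(1 − p)]. At p = 0.50, u = 0.693 and the result is 0.3466² / 0.25 = 0.480, a loss of 52%.

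The range is 34% to 66%. Matching the precision of the dioptre value would take between 1/0.66 = 1.5 and 1/0.34 = 2.9 times as many eyes.

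**Step 2: the paired comparison.** Assumptions: each calculator has a two-dimensional error per eye, with component SD 0.25 to 0.35 D; one calculator's error is 25% larger; the correlation within an eye is 0.70 to 0.85; eyes are independent. With 4,000 simulated data sets per setting and 30 toric eyes:

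- about 6 to 11 eyes are discordant at 0.50 D;
- the squared signal-to-noise ratio is 1.7 to 2.8 times larger on the dioptre scale, a loss of 1 − 1/1.7 = 41% to 1 − 1/2.8 = 64%.

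**Step 3: precision of the proportions themselves.** Exact 95% intervals if 80% of eyes met the cut, eyes treated as independent:

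- 16 of 20: 56% to 94%
- 32 of 40: 64% to 91%
- 48 of 60: 68% to 89%

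Correlation between the two eyes of a patient would usually widen these.

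**Step 4: which continuous quantity helps.** Section 5.3 does not define residual astigmatism, and there are three readings.

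1. *Observed Visit 3 cylinder.* Each eye has one lens and one observed value, so the within-eye difference between calculators is zero on either scale.
2. *Calculator output on the day of surgery.* These are predictions. Comparing them does not show which was more accurate.
3. *Prediction error, observed against predicted.* This differs between calculators and measures accuracy. It is what step 2 models, and section 3.4 collects its components.

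Only the third supports a continuous comparison of the calculators.

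**The case against.** The strongest case on the other side is that this is partly a preference. A proportion within 0.50 D can be the quantity of interest in its own right, and endpoints a to e use the same ±0.50 D form. The proportions would also not hide a difference of the size simulated. Under the step 2 model with component SD 0.30 D, the share within 0.50 D is 1 − exp[−0.25 / (2 × 0.30²)] = 75%. With a 25% larger error (SD 0.375 D) it is 59%. That gap of 16 points would be visible in a descriptive table. This stands, and it is why the proportions should be kept.

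A reader might infer three stronger things that the documents do not support.

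- *That about half the information is thrown away.* The dioptre values stay in the database and section 5.2 excludes no summary of them. Under the normal shift model the loss is near one half (45% to 55%) only if about 74% to 83% of eyes meet the cut, or the mirror range of 17% to 26%.
- *That the plan lacks power.* In the step 2 simulation at 30 eyes, an exact McNemar test on the cut detects the difference 21% to 27% of the time, against 55% to 81% for a paired t-test on the magnitudes. But the plan specifies neither test, nor any formal comparison of f with g. The exact McNemar test is also conservative at this size, and a 25% error difference is an assumed effect. With a smaller one the continuous comparison would often miss it too.
- *That similar f and g results would be uninterpretable.* That presupposes a test. Descriptively they would be imprecise.

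**Conclusion.** The point holds as a cheap improvement. The plan evaluates the two toric calculators only through a yes/no at 0.50 D, while the values and axes needed for a more precise comparison are already collected. The cost is roughly one third to two thirds of the information. This rests on an assumed 50% to 90% of eyes meeting the cut and on assumed error distributions; the paired comparison adds an assumed error ratio and within-eye correlation. None of these, nor the number of toric eyes, is in the documents. It is a loss of precision in a descriptive pilot. The gain in comparing calculators depends on using prediction error; the other two readings of residual astigmatism would not deliver it.

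**What to change.** In sections 5.2 and 5.3, keep the two 0.50 D proportions and add the following.

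- **Quantity.** For each toric eye and each calculator, the astigmatic prediction error in dioptres: the magnitude of the vector difference between the Visit 3 manifest cylinder and that calculator's predicted residual astigmatism and axis for the lens implanted. With C the cylinder and α its axis, write each as (C cos 2α, C sin 2α), subtract, and take the length. Subtracting cylinder magnitudes alone would count equal cylinders at different axes as agreement.
- **Summary.** Mean and median per calculator, and the within-eye mean difference between calculators over the same eyes.
- **Interval.** A 95% interval for that difference that allows for two eyes per patient, for example from a bootstrap that resamples patients.
- **Counts.** The number of toric eyes and of patients contributing them.

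The cost is a few sentences and a little more analysis work, with no new visit, measurement or patient. The proportions remain available for comparison with other reports. The intervals will still be wide if few eyes are toric.

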#### 5.4. Safety Analyses

The type, severity, duration and frequency of reported ocular adverse events will be tabulated. Adverse events will also be summarized for events that were considered treatment-related.

10

#### 6. DATA HANDLING AND RECORD KEEPING

#### 6.1. Confidentiality

To ensure confidentiality in this study, records of the participants will be examined only by the principal investigator and research staff involved in the study. Study records will be kept on file. Any statistical analysis and publication will not include any subject identifiers. Medical records will be made available only for review by the investigators, Sponsor Company or Research Institution, the IRB, and other State or Federal Regulatory Agencies, if necessary. All information in these records will be kept confidential.

#### 6.2. Records Retention

The PI is accountable for the integrity, retention and security of all study related data. The investigator must maintain accurate, complete and current records relating to the clinical study. The investigator must maintain the required records during the investigation and for a period of 2 years after the date on which the investigation is terminated or completed. Records will be scanned and kept electronically in a secured server.

#### 7. STUDY MONITORING, AUDITING, AND INSPECTING

The nature and location of all source documents will be identified to ensure that original data required to complete the case report forms (CRFs) exist and are accessible for verification. If electronic source records are maintained, these records must be 21 CFR Part 11 compliant and will be printed and certified for verification as needed.

Required examination must be recorded on the CRFs. CRFs will be used as source document. All data reported must have corresponding entries in the source documents. The principal investigator or sub-investigator must review the reported data and certify that the CRFs are accurate and complete. No subject identifiers should be recorded on the CRFs beyond subject number, subject initials and study specific identifiers.

Data from CRFs will be entered into a database. Upon completion of the CRFs, the data will be reviewed by study designated personnel and statistician for accuracy and completeness. If corrections and/or any additions to the data are deemed necessary, queries will be generated. Designated research staff expected to respond to data queries in a timely manner and ensure that the corrections and changes made to the data in the database are reflected in the subjects' source documentation. Any changes will need to be initialed and dated by the authorized personnel making such changes.

Data will not be sold to third parties.

